6.3.1.1.2. Secondary Analyses

Incidence rate of AECOPD

The following incidence rates of AECOPD (any type) occurring from enrolment up to 1 month post-Dose 2 will be computed together with 95% CIs, and incidence rates together with VE in the prevention of AECOPD (any type) will be computed over a period starting 1 month post-Dose 2 and lasting for 1 year, with 95% CIs:

- Any severity of AECOPD.
- AECOPD, by event severity.

Time to first AECOPD event

The time to first AECOPD events following complete schedule vaccination (i.e., 1 months post-Dose 2) will be analysed using Cox's proportional hazard regression model which include, with treatment, GOLD grade at enrolment (2, 3 or 4) and history of exacerbations (<2 or ≥ 2) as factors. Wald test and CIs will be produced.

The time to first event will be computed for the following:

- Time to first moderate and severe AECOPD
- Time to first any severity AECOPD.
- Time to first AECOPD, by event severity.

Hazard rate and CI will be derived using the following SAS code:

```
PROC PHREG data=<dataset>;
  CLASS trt age gold hexac;
  MODEL survtime*status(0)=trt age gold hexac / TIES=EXACT RISKLIMITS;
  RUN;
```

In addition the survival curves for each vaccine group will be calculated non-parametrically, and presented graphically using the Kaplan-Meier (i.e., Product-Limit) method, using the following code:

```
PROC LIFETEST data=<dataset> method =KM plot=(survival(atrisk)
  logsurv);
  TIME survtime*Status(0);
  STRATA trt;
  RUN;
```

CONFIDENTIAL

207489 (NTHI MCAT-002)

Statistical Analysis Plan Amendment 2 FDA Final Draft

survtime represents variable containing AECOPD times.

status represents censoring variable (0=censored, 1=event).

Duration of AECOPD event

The length (in days) of each AECOPDs will be tabulated and presented via descriptive statistics (mean, SD, median, Q1, Q3, minimum and maximum), for each treatment and for the two periods (before 1 month post-Dose 2 and after 1 month post- Dose 2).

Tables will be produced considering the following:

- Duration of moderate and severe AECOPDs.
- Duration of AECOPDs of any severity.
- Duration of AECOPDs, by severity.

Stratification and additional analysis

Yearly rate of AECOPD and VE, together with 95% CIs, will be computed for the following time periods:

- By 6 Months follow-up period (from 1 month post-Dose 2)
- By 3 Months follow-up period (from 1 month post-Dose 2)

Similarly, for the time-to-event and duration of AECOPD data will be also presented for the entire study period starting from Day 1 up to study termination.

In addition, descriptive statistics for the yearly rates and VE will be presented by patient severity (GOLD grade: 2, 3, or 4), by Country (USA, Canada, France, Spain, Belgium, UK, Germany and Italy), by history of exacerbations (< 2 or \geq 2), by usage of inhaled corticosteroid at visit 1 (independently on the start date of usage), by eosinophil level at baseline (<2% or \geq 2%), by NHTi and Mcat presence in sputum at baseline (NTHi alone, Mcat alone, NTHi or Mcat) and by age group (40 - 59 yrs or 60 - 80 yrs).

In addition to the rates of moderate and severe and any severity AECOPD at 3, 6, 9 and 12 months starting 1 month post dose 2, the Kendall-Tau (Kendal Rank correlation Coefficient) test for trend of rates over time will be calculated. A statistically significant correlation between Incidence rates and time period will be concluded if p-value is less than 0.05.

A SAS code similar to the following will be used for this purpose:

```
PROC CORR data=<dataset> kendall;  
class treatment;  
  var rate month;  
by treatmens;  
RUN;
```

CONFIDENTIAL

207489 (NTHI MCAT-002)

Statistical Analysis Plan Amendment 2 FDA Final Draft

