2. STUDY DESIGN

Figure 1 Study design overview

S = Screening Visit; V = Visit; PC = Phone contact; D = Day; FU = Follow-up; BS (1) = blood sample for humoral immunogenicity; BS (2) = blood sample for cell-mediated immunogenicity (CMI), this blood sample will only be collected from a sub-cohort of subjects; BS (3) blood sample for biomarkers; SP = sputum sample

The allowed maximum interval between Screening Visit and Visit 1 is 29 days. If a delay occurs for an eligible subject so that the interval exceeds 29 days, some study procedures performed during the Screening Visit needs to be repeated within 7 days (see Table 6 of the protocol for more details).

* An AECOPD visit should be scheduled as soon as possible after the onset of AECOPD symptoms (max 96 hours after and, if applicable, preferably before starting treatment with antibiotics) During this visit blood and sputum samples will be collected. In addition, follow-up phone call(s) and/or visit(s) will take place to determine the end of the AECOPD. These contacts will take place at least every 2 weeks until the AECOPD is resolved.

Investigational vaccine and placebo will be administered in addition to standard of care.

- **Experimental design:** Phase IIB, randomised, observer-blind, placebo-controlled, multi-centric study with two parallel groups.
- **Duration of the study:** for each subject enrolled, the study will last approximately 15 months from Visit 1 up to study completion (Visit 8).
 - Epoch 001: Screening Visit (Day -28 to Day -1).
 - Epoch 002 : Primary starting at Visit 1 (Day 1) and ending at Visit 8 (Day 451).
- **Primary completion Date (PCD):** Last Subject Last Visit (LSLV) from Visit 8 (Day 451) or last visit/contact of Epoch 002.
- **Study groups:**
 - **10-10-3-AS:** Approximately 300 subjects receiving two doses of the AS01_E-adjuvanted GSK Biologicals' NTHi-Mcat investigational vaccine containing 10 µg of PD, 10 µg of PE-PilA, and 3.3 µg of UspA2.
 - **CONTROL:** Approximately 300 subjects receiving two doses of placebo (PBS).

CONFIDENTIAL

207489 (NTHI MCAT-002)

Statistical Analysis Plan Amendment 2 FDA Final Draft

The following group names will be used for the statistical analysis

Table 1 Study groups and epochs foreseen in the study

Group order in tables	Number of subjects	Group label in tables	Group definition for footnote
1	~300	10-10-3-AS	2 doses of AS01E-adjuvanted NTHI/Mcat vaccine containing 10 mcg of PD, PE-PiA and 3 mcg of UspA2

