6.3.1.1. Efficacy – Clinical Endpoints**6.3.1.1.1. Primary Analyses**

The primary analysis method of the vaccine VE will consider the exact inference on the risk ratio (R_{vacc} / R_{con}) based the total number of moderate and severe AECOPD observed in 1 year time of follow up.

VE is defined as: $VE = 1 - R_{vacc} / R_{con}$

being

- R_{vacc} = average yearly incidence rate of AECOPD events per subject in the group 10-10-3-AS.
- R_{con} = average yearly incidence rate of AECOPD events per subject in the placebo group.

Inferential statistic

Incidence rates and VE with 87% and 95% CIs will be tabulated for primary efficacy endpoint. P-value (to test $H_0 = [VE=0]$) will be tabulated for the primary endpoint.

The efficacy of vaccine in preventing moderate and severe AECOPD will be demonstrated if the lower limit of the two-sided 87% CI of VE is above 0.

The primary outcome will be analysed using the Negative Binomial regression model with number of AECOPD as dependent variable; treatment (vaccine or placebo), age group (40 - 59 yrs or 60 - 80 yrs), GOLD grade (2, 3 or 4) and history of moderate and severe exacerbations (<2 or ≥ 2) and country as independent variables, with logarithm as link function, and the logarithm of time for follow-up (in days) as an offset variable.

The following SAS code will be applied for primary analysis:

```
PROC GENMOD data=<dataset>;
  CLASS trt age gold hexac country;
  MODEL nb_exac = trt age gold hexac country
    / dist=NegBin LINK=log OFFSET=logfu alpha=0.13;
RUN;
```

Where

trt= treatment arm;
 age= Age Group;
 nb_exac=number of exacerbations;
 gold= GOLD grade at enrolment;
 hexac= History of moderate/severe exacerbation;
 country=Subject Country;
 fu= follow up time in days;
 logfu= log(fu);

CONFIDENTIAL

207489 (NTHI MCAT-002)

Statistical Analysis Plan Amendment 2 FDA Final Draft

Point estimate and CIs of the incidence rate for each arm, will be computed using a simple Negative Binomial model, without covariates and thus the following SAS code will be applied:

```

PROC GENMOD data=<dataset>;
BY trt;
MODEL nb_exac =           / dist =NegBin LINK=LOG OFFSET=LOGFU alpha=0.05;
ODS OUTPUT ParameterEstimates=out_parm NObs=Nobs;
RUN;

DATA parm_est(keep= val rate rate_LL rate_UL);
SET out_parm(WHERE=(Parameter='Intercept'));
format rate rate_LL rate_UL 8.2;
val= "Yearly Rate from Negative Binomial";
rate=EXP(Estimate)*365;
rate_LL=EXP(LowerWaldCL)*365;
rate_UL=EXP(UpperWaldCL)*365;
RUN;

```

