11.3. Randomization method and minimization algorithm

Subjects are randomised using a centralised randomisation system on internet (SBIR) at first dose. The system incorporates a minimization algorithm based on White SJ and Freedam LS method [[White SJ](#), Freedman LS, 1978] and it is described below:

Notation:

- k input values to be used for minimization, each with a weight w_k ($k=1, \dots, K$) and l_k variants.
- i treatment groups applicable to stratum the subject has been identified with randomization ratio a_1, \dots, a_i
- D: percentage of determinism
- W: weight assigned to each minimization factor

In this study k=4: Country, GOLD grade, History of exacerbation and Age group defined as :

COUNTRY [8 variants]: BE CA FR DE IT ES UK US

GOLD [3 variants]: 2 3 4

AGECAT [2 variants]: 40-60 61-80

HIST_ES [2 variants]: < 2 >=2

i=2: VACCINE and PLACEBO with randomization ratio 1:1 ($a_i=1$)

D=90%

W=1 for each variable

CONFIDENTIAL207489 (NTHI MCAT-002)
Statistical Analysis Plan Amendment 2 FDA Final Draft

Algorithm:

For a new subject in criteria levels $s_1 \dots s_k$ **Step 1: Minimization computation**

Step 1.1: Initialize Problem flag to 0

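### The Cox model for time to first AECOPD leaves out country, a minimisation factor that the primary model adjusts for, and its text and SAS code disagree on age

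*SAP*

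**What the plan says.** All references are to the current SAP (Amendment 2).

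- **Allocation (section 11.3).** "In this study k=4: Country, GOLD grade, History of exacerbation and Age group defined as" four listed variables, with country entered as "COUNTRY [8 variants]: BE CA FR DE IT ES UK US". Each factor has weight 1 and the algorithm is 90% deterministic.
- **Primary analysis (section 6.3.1.1.1).** The negative binomial model uses all four factors, and text and code agree: "MODEL nb_exac = trt age gold hexac country". The count model for PCR-associated events in section 6.3.1.2 has the same covariates.
- **Time to first AECOPD (section 6.3.1.1.2), text.** A Cox "proportional hazard regression model which include, with treatment, GOLD grade at enrolment (2, 3 or 4) and history of exacerbations": no age, no country.
- **Time to first AECOPD, code.** "MODEL survtime*status(0)=trt age gold hexac / TIES=EXACT RISKLIMITS": age is present, country is not.

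The Cox analysis is to yield a Wald test and confidence intervals, and section 7 puts efficacy analyses other than the primary at a 5% level without multiplicity adjustment. Sections 6.3.1.2 and 6.3.1.3 call for time-to-first analyses of PCR- and culture-associated events without giving a separate Cox model, so I take this one to apply there too.

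**The concern.** There are two separate faults.

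First, the text and the code describe different models for the same endpoints. A programmer following one would report a slightly different hazard ratio and p-value from a programmer following the other.

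Second, both versions drop a factor on which allocation was balanced. The SAP keeps that factor in the count models and in the antibody ANCOVA (section 6.4.1), and gives no reason for treating the Cox model differently. In a Cox model, omitting a prognostic covariate pulls the treatment hazard ratio toward 1 compared with the covariate-adjusted value. When allocation has been balanced on that covariate, the model-based standard error is also too large for the design, so the test is conservative. The re-randomisation test, which would respect the minimisation, is specified only as a sensitivity analysis of the primary result.

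At stake is precision and power for a set of inferential secondary results: time to first moderate or severe, any-severity and by-severity AECOPD, and their bacteriological counterparts.

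**Working it through.** **Own figure of the plan.** There is none to reproduce. The SAP states no power, event count, effect size or country effect for time to first AECOPD. The size was therefore examined by simulation over a range of assumptions.

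**Inputs from the SAP.** About 300 subjects per group (section 2); "VACCINE and PLACEBO with randomization ratio 1:1", four minimisation factors, weight 1, 90% determinism, eight countries (section 11.3); one year of efficacy follow-up (section 4.1); two-sided 5% level (section 7).

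**Assumptions, not in the SAP.** Placebo hazard 1.0, 1.2 or 1.5 per year; true conditional hazard ratio 0.75; 10% dropout, uniform over the year; equal country sizes; log-hazard effects of 0.2 per GOLD grade and 0.6 for history. The between-country SD of log hazard was 0, 0.2, 0.4 or 0.6 (extreme countries about 1-, 1.8-, 3.4- and 6-fold apart), paired with an age log hazard ratio of 0, 0.1, 0.2 or 0.3.

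**Model.** Subject hazard = rate × exp(log HR × treatment + country + GOLD + age + history) ÷ mean of exp(covariate terms), with exponential event times. Three Cox models were fitted to each data set: *text* (no age, no country), *code* (age, no country) and *full* (age and country). Power is the share of 800 trials with z < −1.96.

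| Placebo rate | Country SD | HR text | HR full | Power text | Power code | Power full | Full − text |
|---|---|---|---|---|---|---|---|
| 1.0 | 0 | 0.744 | 0.741 | 75.7% | 76.0% | 76.4% | 0.7 |
| 1.0 | 0.2 | 0.753 | 0.748 | 71.0% | 71.3% | 73.0% | 2.0 |
| 1.0 | 0.4 | 0.761 | 0.746 | 67.7% | 68.0% | 72.4% | 4.7 |
| 1.0 | 0.6 | 0.772 | 0.746 | 58.5% | 59.6% | 70.3% | 11.8 |
| 1.5 | 0 | 0.747 | 0.745 | 82.5% | 82.6% | 82.6% | 0.1 |
| 1.5 | 0.2 | 0.754 | 0.748 | 82.1% | 81.9% | 82.8% | 0.7 |
| 1.5 | 0.4 | 0.771 | 0.752 | 72.4% | 72.5% | 79.4% | 7.0 |
| 1.5 | 0.6 | 0.775 | 0.743 | 69.0% | 69.1% | 80.2% | 11.2 |
| 1.2, frailty variance 0.6 | 0.4 | 0.794 | 0.786 | 53.1% | 53.6% | 55.1% | 2.0 |
| 1.2, frailty variance 0.6 | 0.6 | 0.801 | 0.786 | 43.8% | 44.3% | 52.4% | 8.6 |

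The Monte Carlo standard error of one power figure near 70% is √(0.7 × 0.3 ÷ 800) = 1.6 points. The models share data sets, so the differences are better determined than that.

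**Age alone.** Text and code differ by at most 0.001 in hazard ratio and 1.1 power points (59.6 − 58.5). Nearly all of the loss comes from country.

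**Type I error.** With a true hazard ratio of 1, rate 1.2 and 1,200 trials, two-sided rejection at country SD 0, 0.4 and 0.6 was 4.8%, 4.5% and 2.6% for the text model, against 5.1%, 5.4% and 3.7% for the full model. The standard error at 5% is √(0.05 × 0.95 ÷ 1200) = 0.6 points.

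**The case against.** The strongest reply is that nothing in the SAP shows country to be prognostic once GOLD grade and history are in the model. Severity follows one common definition, and differing care or coding between countries is conjecture. With no country effect the loss is immaterial, and at an SD of 0.2 it is at most 2 points. Unexplained heterogeneity, which the negative binomial model itself allows for, shrinks the loss further: at SD 0.4 it falls to 2.0 points. This stands, and it is why no single figure can be attached to the point. It does not explain why a factor thought worth minimising on and adjusting for elsewhere is dropped here.

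It can also be said that the age mismatch is editorial. The SAP states that the hazard ratio will come from the code, which includes age, and the hazard-ratio table template in the appended Amendment 1 SAP lists age. That is fair as to size, but the text still needs correcting.

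A reader might infer more than the documents support:

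- **That the hazard ratio is biased.** The shift reflects non-collapsibility. The less-adjusted hazard ratio is a different quantity from the covariate-adjusted one, not a biased estimate of its own target.
- **That adding country would bring the Cox result into line with the primary vaccine efficacy.** It would not. One is a hazard ratio for the first event and the other a rate ratio over all events, whatever the covariates.
- **That the trial's conclusion is at risk.** Success rests on the primary model's 87% interval alone.

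**Conclusion.** The inconsistency is certain. Country is missing from both versions of the Cox model, age is missing from its text, and no reason is given. If country is prognostic, the reported hazard ratio lies nearer 1 than the covariate-adjusted one and the Wald test is conservative.

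The amount depends on a country effect that the SAP does not give. Under the stated assumptions, the power loss is about nil with no country effect, 1 to 2 points at SD 0.2, 2 to 7 at SD 0.4 and 9 to 12 at SD 0.6, counting the frailty scenarios. The corresponding shift in hazard ratio at SD 0.2 to 0.6 is about 0.005 to 0.03. The upper end needs roughly 6-fold differences between extreme countries. To say flatly that the plan loses power would go beyond what the documents show.

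The error is in the cautious direction, so no false claim of efficacy becomes more likely. It is worth correcting as a cheap improvement to an inferential secondary analysis.

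**What to change.** State one Cox specification, identical in text and code, and refer to it from sections 6.3.1.2 and 6.3.1.3 so that it covers the clinical, PCR and culture time-to-first analyses. The terms are treatment, age group, GOLD grade, exacerbation history and country, coded as in the primary model. In the code this means adding country to the CLASS and MODEL statements; in the text, adding age group and country to the list of factors.

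Where events per country are sparse, as they may be for severe-only events or the culture subset, country may be a STRATA term instead. That avoids estimating seven country coefficients (8 − 1), at the small price that strata with few events contribute little information. Name those analyses in advance. Stratification is an option, not a requirement, and it departs slightly from the primary model's form.

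Keep the primary model's age groups (40–59 and 60–80). Section 11.3 lists 40–60 and 61–80 for the minimisation, and changing the cut in the Cox model alone would create a fresh inconsistency.

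The cost is one sentence and a small code edit, with no new data: country is already collected and used in the primary analysis.

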7. ANALYSIS INTERPRETATION

The primary objective analysis (efficacy) of this study will be evaluated at alpha error of 13% (two-sided test) which is the measurement of the accuracy of our estimation.

Also 2-sided 95% CIs will be provided to show the precision of estimation.

For the secondary objectives we have the following:

- Inferential analyses for primary analysis of efficacy are planned to be performed at alpha level of 0.13 (two sided). No alpha adjustment for multiple testing in the secondary endpoints will be performed, and only the 2-sided 95% CIs will be provided
- All other efficacy and immunogenicity analyses are planned to be performed at alpha level of 0.05 with no adjustment for multiplicity.

CMI and safety analyses are intended to be descriptively only.

All tertiary objectives are exploratory and a p-value <0.1 is considered as reference for statistical significance in comparative analysis. Those comparisons should be interpreted with caution.

CONFIDENTIAL

207489 (NTHI MCAT-002)

Statistical Analysis Plan Amendment 2 FDA Final Draft

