8. CONDUCT OF ANALYSES

The analysis planned in this study will be performed in four steps giving higher priority to the most relevant objectives (i.e., primary, secondary)

Specifically, the analyses will be released in this order:

- Priority 1 analyses will be released at first and reported in a full clinical study report (CSR), this analysis is performed in to two steps:
 - Step 1: Analysis of primary efficacy endpoint and secondary safety endpoint.
 - Step 2: Analysis of immunogenicity, CMI and bacteriological PCR secondary endpoints plus the following tertiary objectives:
 - To evaluate the effect of the investigational vaccine on the presence and load of NTHi and/or Mcat at stable visits and AECOPD by PCR.
 - To explore the impact of the investigational vaccine on health-related quality of life (HRQOL).
 - To explore the T helper profile of the PD-, PE-, PilA-, UspA2-specific CD4+/ CD8+ T cell responses
- Priority 2 analysis will be released in a third step and reported in to an Annex report. They include, the following tertiary objectives:
 - *To evaluate the effect of the investigational vaccine on the presence, acquisition/apparition and load of NTHi and/or Mcat at stable visits and AECOPD by culture.*
 - *To evaluate the effect of the investigational vaccine on the presence, acquisition/apparition and load of NTHi and/or Mcat at stable visits and AECOPD by culture. To explore the efficacy of the investigational vaccine as compared to placebo with respect to the rate of all AECOPDs and by severity (i.e. mild, moderate or severe) associated with NTHi and/or Mcat detected in a subset of sputum samples by culture.*
 - *To explore the impact of the investigational vaccine on use of medication for COPD and Healthcare Resource Utilization.*
 - *To explore the impact of the investigational vaccine on lung function.*
 - *To describe selected biomarkers in stable COPD and during AECOPD*

and other stratified analyses to evaluate VE in subsets:

- Vaccine efficacy (clinical and bacteriological) by eosinophil level in blood at baseline
- Vaccine efficacy (clinical and bacteriological) by NTHi presence in sputum (detected by PCR) at baseline
- Vaccine efficacy (clinical and bacteriological) by Mcat presence in sputum (detected by PCR) at baseline

CONFIDENTIAL

207489 (NTHI MCAT-002)

Statistical Analysis Plan Amendment 2 FDA Final Draft

- Vaccine efficacy (clinical and bacteriological) by NTHi or Mcat presence in sputum (detected by PCR) at baseline

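### Baseline carriage subgroups are defined differently in SAP Sections 6.3.1.1.2 and 8, neither names non-carriers, and subgroup VE is shown with no estimate of the difference between levels

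*SAP*

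**What the plan says.** In the current plan (Amendment 2), the subgroup sentence of Section 6.3.1.1.2 opens "In addition, descriptive statistics for the yearly rates and VE will be presented by patient severity (GOLD grade: 2, 3, or 4), by Country". It continues with exacerbation history, inhaled corticosteroid (ICS) use at Visit 1, baseline eosinophils, baseline carriage and age. The last two items read "by NHTi and Mcat presence in sputum at baseline (NTHi alone, Mcat alone, NTHi or Mcat) and by age group". The sentence attaches no test, interval or decision rule to these displays.

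Section 8 schedules part of this work as Priority 2, introduced as "and other stratified analyses to evaluate VE in subsets". One entry is "Vaccine efficacy (clinical and bacteriological) by NTHi presence in sputum (detected by PCR) at baseline". Parallel entries cover Mcat presence, NTHi or Mcat presence, and blood eosinophils.

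The efficacy count model in Section 6.3.1.1.1, reused for the bacteriological endpoint in Section 6.3.1.2, is "MODEL nb_exac = trt age gold hexac country". It has main effects only. No treatment-by-subgroup term appears in the amendment, and ICS use, eosinophils and carriage are in no efficacy model. Section 7 adds "All other efficacy and immunogenicity analyses are planned to be performed at alpha level of 0.05 with no adjustment for multiplicity".

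**The concern.** Two things are at stake. First, the carriage subgroup is not fixed well enough to program: the class lists in the two sections differ, and the level that carriers would be compared with is not written in either.

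Second, whether VE depends on carriage, ICS use or eosinophils is a question about the difference between levels. Separate VEs, one per level, do not estimate that difference. The plan supplies neither the contrast nor, in Section 6.3.1.1.2, a warning against comparing levels by eye. It does write such warnings for the between-group immunogenicity comparisons (Section 6.4.1), quality of life (Section 6.6.2) and the tertiary objectives (Section 7).

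**Working it through.** The plan states no figure for the subgroup analyses, so there is none to reproduce. Its only error arithmetic, 1 − 0.13 = 0.87 for the primary interval, is consistent and does not bear on this point.

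**1. Carriage classes side by side.** *Alone* can mean exclusively, or each organism taken by itself. *Either* stands for NTHi or Mcat.

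| Baseline status | 6.3.1.1.2, exclusive reading | 6.3.1.1.2, other reading | Section 8, present level |
|---|---|---|---|
| NTHi only | NTHi alone; either | NTHi alone; either | NTHi; either |
| Mcat only | Mcat alone; either | Mcat alone; either | Mcat; either |
| Both | either only | all three | all three |
| Neither | none | none | none (absent level, if one is meant) |

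On the exclusive reading, subjects carrying both organisms move between classes from one section to the other. On either reading, non-carriers have no class in Section 6.3.1.1.2.

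**2. Size of the classes.** Assumptions: NTHi prevalence p = 20 to 40%, Mcat prevalence q = 5 to 20%, independent carriage, 600 subjects (about 300 per arm, Section 2). Neither = (1 − p)(1 − q):
- 0.80 × 0.95 = 0.76, or 456 subjects
- 0.70 × 0.90 = 0.63, or 378
- 0.60 × 0.80 = 0.48, or 288

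Both = pq = 0.01, 0.03 and 0.08, or 6, 18 and 48 subjects.

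**3. Number of levels.** GOLD 3 + country 8 + history 2 + ICS 2 (taken as yes/no) + eosinophils 2 + carriage 3 + age 2 = 22 levels over seven factors.

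**4. What level-wise VEs show when VE is uniform.** Take one factor in equal halves, n = 150 per arm in each half, one year of follow-up, placebo rate μ and negative binomial dispersion k:

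SE(log RR) = √[(1/μ + 1/(μ(1 − VE)) + 2k)/n]

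The chance P that one half is significant at two-sided 5% follows from |ln(1 − VE)|/SE. The chance that exactly one half is significant is 2P(1 − P).

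Worked case, VE = 20%, μ = 0.8, k = 1.0: SE = √[(1.25 + 1.5625 + 2)/150] = 0.179; 0.223/0.179 = 1.246; P = 0.238; 2 × 0.238 × 0.762 = 0.363.

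| μ per year | k | P | Exactly one half significant |
|---|---|---|---|
| 0.8 | 1.0 | 0.238 | 0.363 |
| 0.8 | 0.5 | 0.288 | 0.410 |
| 1.2 | 1.0 | 0.284 | 0.407 |
| 1.2 | 0.5 | 0.364 | 0.463 |
| 2.0 | 1.0 | 0.340 | 0.449 |
| 2.0 | 0.5 | 0.466 | 0.498 |

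Over the same rates and dispersions the figure is 9.5% at VE 0, 17 to 25% at VE 10% and 28 to 50% at VE 30%. A single interaction test at 5% would signal a difference in 5% of trials in all of these cases.

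**5. What the contrast can and cannot do.** With equal halves, the log ratio of rate ratios has SE √2 times the level-wise SE. At VE 20% that is √2 × 0.179 = 0.253 at worst and √2 × 0.119 = 0.168 at best (μ = 2.0, k = 0.5). The 95% CI therefore runs from the estimate divided by to the estimate multiplied by exp(1.96 × 0.253) = 1.64, or exp(1.96 × 0.168) = 1.39. Seven independent 5% tests give 1 − 0.95⁷ = 30% chance of at least one false signal.

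**The case against.** The strongest reply is that the plan calls this output descriptive. That stands. Where a conclusion is intended, Section 6.3.1.1.2 says so: its Kendall trend test has a 0.05 rule, while the subgroup sentence has none and does not mention 95% intervals. A reader might infer that the plan will claim effect modification from these tables, but no section says that. The general 0.05 statement in Section 7 does not turn a descriptive display into a subgroup test.

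A reader might also infer that non-carriers get no VE anywhere, or that carriers cannot be compared with non-carriers at all. Section 8 does not support this: stratifying by presence plausibly means present against absent. Nor do all three listed classes necessarily overlap, since NTHi alone and Mcat alone are disjoint on the exclusive reading.

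New detection in baseline-negative subjects is analysed by arm through the acquisition analyses of Section 6.6.1.2. The carriage and eosinophil splits are Priority 2, listed with tertiary objectives, which Section 7 says to interpret with caution. Interaction tests would also bring multiplicity to a display that now carries no p-values.

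These replies limit the point without removing it. Section 8 gives evaluating VE in subsets as the purpose, the carriage wording remains inconsistent, and the acquisition analyses estimate acquisition, not VE against exacerbations by carriage status.

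**Conclusion.** The point holds in a limited form. The two carriage definitions do not match, the negative level is unwritten in both, and Section 6.3.1.1.2 followed literally leaves out about 48 to 76% of subjects. That range rests on assumed prevalences and independent carriage. Separately, the plan offers no estimate of any between-level contrast for its seven factors. The 36 to 50% figure illustrates why level-wise VEs are a poor substitute. It assumes a uniform VE of 20%, equal halves, rates of 0.8 to 2.0 per year, dispersion of 0.5 to 1.0, and levels judged at 5%. The SAP gives none of the rate, dispersion or VE inputs, and the subgroup sentence does not itself ask for level-wise significance.

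The primary analysis is unaffected. What is at issue is whether the subgroup VEs can be built unambiguously and interpreted.

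**What to change.** - In Section 6.3.1.1.2, define baseline carriage by PCR as four exclusive classes (neither, NTHi only, Mcat only, both), plus any against none. Use the same classes in Section 8.
- For each subgroup factor, fit the primary negative binomial model in all subjects with the factor and a treatment-by-factor term. Report the ratio of rate ratios with 95% CI, and an overall interaction test for factors with more than two levels, labelled exploratory.
- State that no difference between subgroups is inferred from level-wise VEs.

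The cost is SAP wording and one added model per factor. The terms have low power, and seven unadjusted tests carry about a 30% chance of at least one false signal; the report should say both. The class carrying both organisms may be too small for a useful VE (6 to 48 of 600 under the assumptions above), which is why any against none should be kept as well.
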